8.2 Sample Size/Accrual Rate

8.2.1 Sample Size

The required sample size is based upon the primary study hypothesis which is the rate of local recurrence within the spared NPC-containing region at 1 year post radiation therapy in patients treated with NPC sparing RT plus temozolomide for newly diagnosed GBM. Using conventional RT, approximately 20% of GBM recur outside of the tumor bed or radiation field margin (48). We hypothesize that there will be $\leq 25\%$ LR rate in the designated NPC avoidance region using our modified radiation technique, which is clinically acceptable. This is the first study to estimate the LR rate in the spared NPC containing region following NPC sparing RT for GBM. Given the clinically meaningful control LR rate in this region of 25% and a moderate variation among the patients, the 30 patients will have the optimal information gain (relative certainty) based on empirical information entropy to estimate the LR rate in the spared region (49).

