8.2.2 Accrual

We anticipate enrollment of approximately 3-4 patients per month to the protocol with accrual completed in approximately 1-2 years.

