8.4 Statistical Methods of Analysis

All analysis will be based on the Intend-To-Treat (ITT) principle. Per-protocol will be allowed after ITT analyses.

The proportion of patients with LR in the avoidance region of the NPC will be estimated along with the exact 95% confidence interval. The lower bound 95% confidence interval of exact binomial distribution will be used to determine the acceptance of the LR rate of 25%.

All patients will count towards assessment of all objectives. However, if no patient relapses in the spared NPC containing region, we recognize that the present study will not definitively demonstrate that sparing of the NPC regions does not impact the pattern of recurrence since this is a pilot study and 2 patients received mebendazole following completion of radiation therapy but prior to relapse. Given that no intervention to date including systemic agents, radiation dose escalation, and hypofractionation has ever impacted the site of recurrence we feel it is exceedingly unlikely that mebendazole would impact our primary endpoint. However, we will evaluate if the analysis of the primary endpoint would yield different results with or without inclusion of these patients. If there is a difference both analyses will be presented in the manuscript. Even if there is no statistically significant difference

between the groups we will clearly state in our publications that 2 patients received mebendazole with their adjuvant temozolomide following completion of radiation therapy but prior to relapse.

To quantify the extent of radiation dose sparing to the NPC containing regions that is possible, patients will be binned into 4 groups according to the volume of NPC region that receives a certain dose as follows: 1) $V_{5Gy} \le 50\%$; 2) $V_{5Gy} \le 20\%$; 3) $V_{10Gy} \le 20\%$; 4) Doses higher than levels 1-3. The proportion of overall patients who meet at least the dose constraint will be estimated using a binomial distribution along with 95% confidence intervals, as well as the individual group.

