8.5 Interim Disease Progression Monitoring

Based on the unpublished data from the New approaches to Brain Tumor Therapy Consortium, the median time of progression was 8.5 months among the newly diagnosed GBM treated by RT+TMZ (standard). The progression area outside radiation bed was about 20%. This study does not anticipate an above 30% progression rate in the spared NPC containing region. We expect a less than 30%, about 20% progression rate in the spared NPC containing region. However, we plan to monitory the progression rate throughout the trial. The progression rate in the spared NPC containing region will be monitored continuously throughout the cohort using the Bayesian stopping rule at patient numbers 10 and 20, after patients have a minimum of 6 months follow-up. We consider a 30% progression rate the highest limit that permits to continue this study and will stop early if there are excesses. The number of patients experiencing progression in the spared NPC containing region was assumed to follow a binomial distribution. Given the planned sample size of 30, a stopping boundary would be reached if the proportion of patients experiencing progression in the spared NPC containing region exceeds 30% with a posterior probability ≥ 0.6 . A recommendation for early stopping if 4 or more out of 10, or 7 or more out of 20 patients had disease progression in the spared NPC containing region. The probability of meeting the stopping boundary is 0.56 under a true probability of progression is 0.3.

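### Section 8.4 judges a 25% ceiling on recurrence by the lower exact confidence limit, which cannot show that the rate is acceptable

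*Combined protocol and SAP*

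**What the plan says.** Section 1.1 sets the primary objective as estimating the one-year local recurrence rate in the spared region. Section 8.4 plans that estimate: "The proportion of patients with LR in the avoidance region of the NPC will be estimated along with the exact 95% confidence interval". The next sentence adds a decision: "The lower bound 95% confidence interval of exact binomial distribution will be used to determine the acceptance of the LR rate of 25" per cent. It gives no inequality, cut-off count or error rate, and no other section supplies them.

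Section 8.2.1 fixes the direction. It hypothesises a rate of at most 25% and describes that "LR rate in the designated NPC avoidance region using our modified radiation technique, which is clinically acceptable". So 25% is an upper bound on something undesirable.

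Section 8.4 also plans a sensitivity analysis, because "2 patients received mebendazole following completion of radiation therapy but prior to relapse": "we will evaluate if the analysis of the primary endpoint would yield different results with or without inclusion of these patients". It concedes that "the present study will not definitively demonstrate that sparing of the NPC regions does not impact the pattern of recurrence", but only for the case of no relapse in the spared region.

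Section 8.5 separately monitors progression in the same region against a 30% limit, at patients 10 and 20, "after patients have a minimum of 6 months follow-up". It recommends stopping at 4 or more of 10, or 7 or more of 20, and gives a stopping probability of 0.56 at a true rate of 0.30. It lists no boundary at 30 patients.

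**The concern.** A lower confidence limit answers whether the data prove the rate is too high. It does not answer whether the rate is acceptably low. With 30 patients the interval is wide, so the lower limit stays under 25% even when many patients recur. Calling that outcome acceptance turns lack of proof of harm into a favourable finding.

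This is the only criterion stated for the final primary result; 8.5 governs monitoring. Section 2.1 makes a later randomised trial depend on showing no adverse influence on recurrence in the spared region. It does not name the 8.4 rule, so the link from one to the other is an inference. A reader of the eventual report could still take an accepted 25% as meeting that condition.

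**Working it through.** **Inputs.** n = 30 (8.2.1); exact binomial 95% interval and 25% reference (8.4); expected rate about 20%, looks at 10 and 20 patients, boundaries 4/10 and 7/20, stated stopping probability 0.56 at 0.30 (8.5). Section 8.4 specifies intention to treat and counts all patients, so n = 30 is used. The sample size cannot be recomputed, because the moderate variation it rests on is not quantified.

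**1. The plan's own figure, 0.56 in 8.5.** With binomial events at p = 0.30:

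- Look 1: P(X ≥ 4 of 10) = 0.350.
- Look 2: P(at most 3 of 10, then 7 or more of 20) = 0.135.
- Sum: 0.485, not 0.56.
- Adding a third boundary at 30 patients: 9/30 gives 0.642, **10/30 gives 0.561**, 11/30 gives 0.513.

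Of the boundaries tried at 30, only 10/30 matches. The posterior criterion in 8.5 (probability of at least 0.6 that the rate exceeds 30%) points the same way. Under a Beta(1,1) prior, the posterior probability is 0.54 at 9/30 and 0.69 at 10/30. The prior is an assumption, since none is stated; Beta(0.5,0.5) and Beta(0.3,0.7) give the same three cut-offs of 4, 7 and 10.

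**2. Exact limits at n = 30.** Lower = 0.025 quantile of Beta(x, 31 − x). Upper = 0.975 quantile of Beta(x + 1, 30 − x).

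| Recurrences | Observed | Lower | Upper | Lower limit ≤ 25%? |
|---|---|---|---|---|
| 2 | 6.7% | 0.8% | 22.1% | yes |
| 3 | 10.0% | 2.1% | 26.5% | yes |
| 6 | 20.0% | 7.7% | 38.6% | yes |
| 10 | 33.3% | 17.3% | 52.8% | yes |
| 12 | 40.0% | 22.7% | 59.4% | yes |
| 13 | 43.3% | 25.5% | 62.6% | no |

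On the natural reading, 12/30 is accepted and 13/30 is the first count rejected. From 3/30 to 12/30 the verdict is acceptance while the interval extends above 25%. That range includes 6/30, the result at the expected 20%.

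**3. Probability of acceptance.** Final rule alone: P(X ≤ 12 of 30). With interim looks: exact recursion in blocks of 10, continuing only below each boundary, then X ≤ 12. The recursion assumes that both recommendations are followed and that the same events count at interim and final.

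| True rate | Final rule alone | With 4/10 and 7/20 | Also with 10/30 (unstated) |
|---|---|---|---|
| 30% | 0.92 | 0.51 | 0.44 |
| 35% | 0.78 | 0.34 | 0.25 |
| 40% | 0.58 | 0.19 | 0.12 |

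In the last column, passing means fewer than 10 events at 30 patients, so 8.5 and not 8.4 sets the limit.

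**4. Other readings.** If acceptance required a lower limit above 25%, only 13/30 or more would pass, which reverses the intent. If lower is a slip for upper, at most 2/30 would pass two-sided. At the expected 20% that has probability P(X ≤ 2 of 30) = 0.04. Either way the sentence needs changing.

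**The case against.** The best defence is that a lower limit is a legitimate tool here. If a rate of at most 25% is the null hypothesis and excess recurrence the alternative, comparing the lower exact limit with 25% is the standard exact test, and acceptance means only non-rejection. That is a coherent, if permissive, screen for a pilot whose stated aim is to estimate. This stands in part: the calculation is not meaningless. But non-rejection does not establish what 8.2.1 calls clinically acceptable, and the text neither says that non-rejection is meant nor states the inequality.

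Two mitigations also stand. The exact interval will be reported, so a reader can see the upper limit. And 8.5 makes high counts less likely. With both listed boundaries respected on identical events, 12/30 can arise only from at most 6 in the first 20 and at least 6 in the last 10. Neither repairs the rule. The written caveat in 8.4 covers only zero relapses, not the 3 to 12 events for which the verdict misleads.

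A reader might infer that 8.4 and 8.5 flatly contradict each other. The documents do not support that. Section 8.5 concerns progression during monitoring, from a minimum of 6 months; 8.4 concerns recurrence at one year; and a boundary at 10/30 is inferred, not written. A reader might also make much of the unstated sidedness. The preceding sentence points to an ordinary two-sided interval, and at n = 30 a one-sided lower limit gives the same cut-off (24.95% at 12/30).

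**Conclusion.** The point holds as a defect in the decision wording and should be fixed. As written, 8.4 attaches acceptance of a 25% harm ceiling to a limit that can only fail to show an excess. On the natural reading, the rule alone accepts up to 12/30. That cut-off assumes 30 patients counted and acceptance unless the lower limit exceeds 25%; the joint probabilities also assume identical events at interim and final and compliance with the stopping recommendations.

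It would go too far to conclude that the trial as a whole would accept 40% recurrence. If 8.5 intends a boundary at 10/30, counts of 10 to 12 would be flagged there yet accepted under 8.4. This is a reason to reconcile the sections, not proof that the higher counts would pass unnoticed. Nor does it follow that the plan should adopt an upper-limit pass/fail test: at n = 30 and a true 20% such a test would be met about 4% of the time, and some outcomes are already known.

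**What to change.** In 8.4, delete the lower-bound acceptance sentence and keep the proportion with its two-sided exact 95% interval as the primary result. Add wording to this effect:

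> A lower limit at or below 25% means only that the rate was not shown to exceed 25%. A rate of at most 25% is not established while the upper limit is above 25%. A sample of 30 supports estimation of the rate and not its acceptance.

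Apply the same wording to the planned analysis without the two mebendazole patients.

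State how the 25% in 8.4 relates to the 30% limit in 8.5, and whether a boundary at 30 patients is intended, since the listed looks do not give the stated 0.56.

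Date the change and disclose that some outcomes were known when it was made; 8.4 already refers to treatment given before relapse.

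The cost is a few sentences in 8.4 and a clarification in 8.5, with no new patients, data or analyses. The downsides are a less favourable stated conclusion and a late wording change to a primary criterion, which is why the disclosure matters.

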TITLE: A Prospective Trial of Neural Progenitor Cell Sparing Radiation Therapy Plus Temozolomide for Newly Diagnosed Glioblastoma Multiforme

Research Site:	The Johns Hopkins University School of Medicine
Principal Investigator:	[name]., M.P.H. Department of Radiation Oncology [name] [contact] [contact] Email: [contact]
Co-Investigators:	[name]., Department of Radiation Oncology [name]., Department of Medical Oncology [name]., Department of Neuropsychology [name], N.P., Department of Oncology [name]., Department of Oncology [name]., Ph.D., Department of Oncology [name]., Department of Neurosurgery [name]., Department of Neurology [name]., Department of Psychiatry

Statistician:

[name]., M.S. [contact] Email: [contact]

Study Coordinators:

[name] [contact] [contact]

Research Nurses:

[name], R.N., B.S.N. [contact] [contact] [name] [contact] [contact]

[name], R.N.,

[contact]

[contact]

[contact] [contact]

> [name], R.N. [contact] [contact]

[name], B.S.

SCHEMA

Patient Eligibility: (See Section 3)

Newly diagnosed, histologically confirmed glioblastoma multiforme. Radiation and medical oncologist recommends adjuvant radiation plus temozolomide. Must begin therapy within 12 weeks of biopsy or surgery. No prior brain radiation. Age \geq 18 years. KPS > 60%. Signed informed consent.

Treatment Plan: (See Section 5)

Required sample size: 30 patients Anticipated accrual: 4-5 patients per month

TABLE OF CONTENTS

SC	HEM	P	age ii
ыc		•	11
1.	OBJE	CTIVES	1
	1.1	Primary Objectives	1
	1.2	Secondary Objectives	1
2.	BACH	KGROUND	1
	2.1	Study Disease and Rationale	1
	2.2	Temozolomide	3
	2.3	Correlative Studies Background	3
3.	PATI	ENT SELECTION	5
	3.1	Eligibility Criteria	5
	3.2	Exclusion Criteria	6
	3.3	Inclusion of Women and Minorities	6
4.	REGI	STRATION PROCEDURES	6
5.	TREA	ATMENT PLAN	7
	5.1	Surgery and Chemotherapy	7
	5.2	Radiation	7
	5.3	Duration of Follow Up	9
	5.4	Criteria for Removal from Study	9
6.	STUE	DY CALENDAR	10
7.	MAN	AGEMENT OF TOXICITY	11
	7.1	Acute Toxicity	11
	7.2	Late Toxicity	13
8.	STAT	ISTICAL CONSIDERATIONS	14
	8.1	Study Design/Endpoints	14
	8.2	Sample Size/Accrual Rate	15
	8.3	Stratification Factors	15
	8.4	Statistical Methods of Analysis	15
	8.5	Interim Disease Progression Monitoring	16
9.	ADVI	ERSE EVENTS AND REPORTING	17
	9.1	Definition of Adverse Event	17
	9.2	Radiation Related Adverse Event	17
	9.3	Chemotherapy Related Adverse Event	18

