3.2 Exclusion Criteria

3.2.1 Patients may not receive any approved or investigational agents to treat their glioblastoma besides temozolomide.

Note: Exceptions may be made for non-therapeutic intervention at the discretion of the Principal Investigator.

- 3.2.2 No prior malignancy is allowed except for adequately treated basal cell or squamous cell skin cancer, cervical carcinoma in situ, or other cancer from which the patient has been disease free for at least 2 years.
- 3.2.3 Patients with uncontrolled intercurrent illness including, but not limited to, ongoing or active infection, symptomatic congestive heart failure, unstable angina pectoris, cardiac arrhythmia, or psychiatric illness/social situations that would limit compliance with study requirements will be excluded.
- 3.2.4 Pregnant and breastfeeding women are excluded. Women of child-bearing potential who are unwilling or unable to use an acceptable method of birth control to avoid pregnancy for the entire study period and up to 12 weeks after the study are excluded. This applies to any woman who has not experienced menarche and who has not undergone successful surgical sterilization or is not postmenopausal (defined as amenorrhea for at least 12 consecutive months). Male subjects must also agree to use effective contraception for the same period as above.

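### The primary analysis without the two mebendazole patients is shown only if it differs, and leaving them out barely tests whether the drug lowered the 1-year recurrence rate

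*Combined protocol and SAP*

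**What the plan says.** Section 3.2.1 states "Patients may not receive any approved or investigational agents to treat their glioblastoma besides temozolomide", with a discretionary exception for non-therapeutic interventions. Section 5.1.2 opens further chemotherapy or biologic therapy at progression or after one year of follow-up. Section 8.4 records that two patients received mebendazole with adjuvant temozolomide, after radiotherapy and before relapse.

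Section 8.4 handles these two patients as follows:

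- They stay in: "All patients will count towards assessment of all objectives".
- Their inclusion is defended on the ground that no intervention so far has altered where glioblastoma recurs.
- One check is planned: "we will evaluate if the analysis of the primary endpoint would yield different results with or without inclusion of these patients".
- Presentation of that check is conditional: "If there is a difference both analyses will be presented in the manuscript".
- The mebendazole use will be stated in publications whether or not a significant difference is found.

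The primary proportion "will be estimated along with the exact 95% confidence interval". The decision rule is: "The lower bound 95% confidence interval of exact binomial distribution will be used to determine the acceptance of the LR rate of 25" percent. Whether the bound is one-sided or two-sided is not stated, and neither is the direction of acceptance. Section 8.2.1 calls a rate of up to 25% in the avoidance region one "which is clinically acceptable". The schema gives "Required sample size: 30 patients".

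**The concern.** There are three linked weaknesses.

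1. **Result-dependent reporting.** Whether a reader sees the estimate without these two patients depends on what that estimate turns out to be, judged by an undefined criterion. That is a selective-reporting rule written into the plan.
2. **The rationale answers a different question.** Constancy of the site of recurrence does not imply constancy of the proportion recurring in the spared region by one year.
3. **The check is weak where it matters.** The worrying bias is that an added agent suppressed or delayed recurrence, so that the rate looks too low. If so, the two patients are event-free at one year, and removing event-free patients changes little.

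Section 2.1 makes an acceptable recurrence result the condition for planning a randomised trial, so a rate that looks low for the wrong reason has consequences.

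**Working it through.** The plan states no figure for this check, so there is none to reproduce.

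**Inputs.** N = 30 (schema); 2 affected patients (Section 8.4), leaving 28; limit 25% (Sections 8.2.1 and 8.4); exact binomial 95% interval (Section 8.4). Assumptions: two-sided limits unless stated otherwise, and acceptance unless the lower limit exceeds 25%.

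**Formulas.** For x events in n patients, lower = Beta quantile(0.025; x, n − x + 1) and upper = Beta quantile(0.975; x + 1, n − x). With x = 0, upper = 1 − 0.025^(1/n).

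**Step 1: site against rate.** Section 8.1.2 records the site of recurrence at one year in three classes, the third being no local recurrence. Sections 1.1 and 8.2.1 make the target a 1-year rate, and Section 8.4 estimates a proportion. A patient whose spared-region recurrence is delayed past one year moves from class 1 to class 3. The eventual site is unchanged and the proportion falls. Section 8.5 quotes a median time to progression of 8.5 months on standard treatment, so the 1-year cut lies where delay can matter. The largest effect two patients can have on the full-sample proportion is 2/30 = 6.7 percentage points.

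**Step 2: what exclusion shows when both patients are event-free.** With x = 0, the upper limit is 1 − 0.025^(1/30) = 11.6% for 30 patients and 1 − 0.025^(1/28) = 12.3% for 28. The table adds small event counts and the bound in which both patients are counted as events.

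| Observed | Upper limit, all 30 | Upper limit, without the two | Bound | Upper limit, bound |
|---|---|---|---|---|
| 0 | 11.6% | 12.3% (0/28) | 2/30 | 22.1% |
| 1 | 17.2% | 18.4% (1/28) | 3/30 | 26.5% |
| 2 | 22.1% | 23.5% (2/28) | 4/30 | 30.7% |

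Exclusion moves the upper limit by about 0.8 to 1.4 points; the bound moves it by about 9 to 10.5 points.

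**Step 3: does exclusion of two event-free patients change the decision?** At N = 30 with two-sided limits, it does not. The lower limits are 22.7% for 12/30 and 24.5% for 12/28 (both accept), and 25.5% for 13/30 and 27.5% for 13/28 (both reject). Rejection therefore starts at 13 events for both sample sizes.

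**Step 4: how far that depends on the reading.**

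- One-sided 95% bound, N = 30: 12/30 has lower limit 24.95% (accept) and 12/28 has 26.9% (reject).
- Two-sided, N = 29: 12/29 is 23.5% (accept) and 12/27 is 25.5% (reject).
- Two-sided, N = 31: 13/31 is 24.6% (accept) and 13/29 is 26.5% (reject).
- Two-sided, N = 28: 12/28 is 24.5% (accept), while rejection at n = 26 starts at 12 events.

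The result in Step 3 belongs to exactly N = 30 with two-sided limits. It is not a general property of the rule.

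**The case against.** The strongest reply is that Section 8.4 is already candid. It discloses the mebendazole use unconditionally. It permits a per-protocol analysis after intention-to-treat. It also concedes that, even with no relapse in the spared region, the study would not settle the question, and it gives mebendazole as one reason. All of that stands, so nobody should say that the drug use is hidden or that this check is the plan's only safeguard. But disclosing the use is not the same as reporting the estimate and interval without these patients, and the per-protocol analysis is allowed rather than required.

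A second reply is that the condition, read literally, always fires: the interval changes even from 0/30 to 0/28. On that reading the condition has no effect and can be deleted at no loss. On any other reading it filters by result.

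A third is that Section 8.1.2 words the endpoint as a site, so the rationale is not out of place. That is fair, but the quantity estimated and judged is a proportion at one year.

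Four stronger inferences are tempting and should not be drawn.

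- **That exclusion can only turn a rejection into an acceptance.** With two-sided limits at N = 30 the only changes are 13/30 to 12/28, 13/30 to 11/28 and 14/30 to 12/28, and all run that way. Step 4 shows the opposite change under a one-sided bound or another final size. The two-sided changes also need at least 13/30 events. If the stopping boundaries in Section 8.5 are followed, and monitored progression and 1-year recurrence are taken as the same events, that has probability 0.05%, 0.17% and 0.55% at true rates of 25%, 30% and 40%.
- **That a significance test of 2 against 28 patients decides what is shown.** The mention of statistical significance in Section 8.4 belongs to the promise to disclose mebendazole use. No such test is specified as a condition for presenting both analyses.
- **That the bound would overturn the decision.** Moving 6/30 (20.0%) to 8/30 (26.7%) takes the point estimate past 25%, but the lower limit for 8/30 is 12.3%, so the plan's rule still accepts.
- **That the cognitive results need re-analysis.** They are exploratory, and nothing in the documents shows that two patients would distort them.

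**Conclusion.** The concern holds in a limited form. Reporting of the second primary analysis depends on an undefined difference, the stated rationale does not cover a 1-year rate, and exclusion is a poor test of suppressed recurrence. In the plan's own scenario of no spared-region relapse, exclusion moves the upper limit from 11.6% to 12.3%, against 22.1% when both patients are counted as events.

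These figures assume a final N of 30, two-sided exact limits and, for the comparison, that both patients are event-free in the spared region at one year. The documents do not say where or when either patient recurred, and they give no evidence that mebendazole had any effect. The bound is therefore a worst case and not an estimate of bias.

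The conflict with Sections 3.2.1 and 5.1.2 is on the face of the text. It would not arise if the drug began after one year or fell under the non-therapeutic exception, and the documents do not say which applies. The passages should be reconciled.

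**What to change.** In Section 8.4:

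1. Delete the condition on presenting both analyses. State that the primary proportion and its exact 95% interval will always be reported for all patients and without the two mebendazole patients.
2. Add a labelled sensitivity bound that counts as an event either of the two who has no spared-region recurrence at one year; 0/30 would then be shown as 2/30, upper limit 22.1%.
3. State whether the lower bound is one-sided or two-sided and which side of 25% means acceptance, since the effect of exclusion on the decision depends on both.
4. Amend the rationale to acknowledge that an agent that delays progression could lower the 1-year rate without changing any site of recurrence.
5. State how the mebendazole use stands in relation to Sections 3.2.1 and 5.1.2.

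The cost is wording and a few more lines in the results table, with no new data. The bound will look less favourable than the main estimate.
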